#### 1.1.9.3 Intercurrent events

Discontinuation of treatment, both before and during the efficacy period, is considered an intercurrent event and will be handled by the hypothetical strategy.

Different approaches for discontinuation of treatment during the efficacy period are applied for the primary and the secondary estimands (see sections **1.1.9.5**, **1.1.9.6** and **1.1.9.7**.). The difference between the primary and the secondary estimands for the primary endpoint is the inclusion or exclusion of data from subjects who discontinue treatment during period 4, respectively.

If a subject discontinues treatment prior to the efficacy period (period 4 for the primary endpoint and visit 5 to visit 11 for the key secondary endpoints), no data from the efficacy period will contribute to the analysis of the primary and secondary estimands.

As only 3 subjects discontinued treatment but did not withdraw from the trial at the time of treatment discontinuation, the discontinuation of trial is not considered with respect to the intercurrent events as it will not add information to make a separate analysis approach (treatment policy estimand) for these very few subjects.

In allergy immunotherapy clinical trials, rescue medication is dispensed to every subject. Therefore, rescue medication is expected to be used as part of the trial design, and hence use of rescue medication is not classified as an intercurrent event.

As all estimands follow the hypothetical strategy, they assess the anticipated effect of the trial product if taken as instructed.

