### 1.1.9.7 Primary estimand for the key secondary endpoints

Variable: Each key secondary endpoint defines a variable for the estimand.

**Population level summary**: The absolute difference in means of the endpoint between treatment with HDM SLIT-tablet and placebo or the ratio between treatment means of the endpoint between treatment with HDM SLIT-tablet and placebo (depends on the definition of each endpoint).

**Intercurrent events (discontinuations) in efficacy period:** Discontinuations in the efficacy period will be handled as for the primary estimand for the primary endpoint. The efficacy period for the key secondary endpoints is defined as visit 5 – visit 11.

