### Figure 1 Overview of trial design

Period 1 is the screening period.

Period 2 is the 3-week baseline period during which eligible subjects will fill in their asthma and rhinoconjunctivitis symptoms and medication use in an electronic diary (eDiary). Only the 2 last weeks of the 3-week baseline period will be used for calculation of baseline scores. At the start of period 2 (visit 2) subjects' regular asthma rescue mediation and rhinoconjunctivitis rescue medication will be replaced with the rescue medication provided by ALK.

Period 3 is the treatment initiation and maintenance period to allow the treatment with the HDM SLIT-tablet to take effect. It starts at randomisation and lasts for 4-10 months. Period 3 ends the 31st of August. During the first 28 days of period 3, 15 prespecified symptoms occurring after IMP intake will be assessed by the subject/parent/caregiver in the eDiary. The reported symptoms will be evaluated by investigator and reported, based on the investigator's medical evaluation and discretion, in the eCRF as solicited AEs.

Period 4 is the efficacy assessment period for the primary endpoint. Period 4 begins on September 1st for all subjects and lasts until the end of trial or discontinuation from IMP. During this period, the rate of clinically relevant asthma exacerbations will be evaluated.

Every 4 months after randomisation, subjects or their parent/caregiver will be asked to complete the eDlary for a period of 14 days 3 weeks prior to V5 (at 4 months), V6 (at 8 months), V7 (at 12 months), V8 (at 16 months), V9 (at 20 months), V10 (at 24 months) and V11 (25-29 months).

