### 3 ANALYSIS SETS

For the purposes of analysis, the following participant analysis sets are defined:

Analysis set	Description
FAS	The FAS consists of all randomised subjects, who received at least 1 dose of IMP. Subjects will be analysed as randomised, i.e. according to their randomised assignment of treatment.
SAF	The SAF consists of all randomised subjects, who received at least 1 dose of IMP. Subjects will be analysed as treated, i.e. according to the treatment they actually received.
PP	The PP will consist of all subjects in FAS without protocol deviations, which may substantially affect the primary endpoint. Subjects will be analysed as randomised, i.e. according to their randomised assignment of treatment.

Before database lock, a list will be made that defines which subjects in FAS are not included in PP and the reason for this. The criteria for not including subjects in PP are the following:

- 1. Violation of the inclusion/exclusion criteria that may potentially impact the primary endpoint
- 2. Use of prohibited medication close to or during the efficacy evaluation period (period 4) that may potentially impact the primary endpoint
- 3. Treatment compliance in the entire trial. Subjects with a treatment compliance below 80% are not included in the PP
- 4. Efficacy compliance. Subjects with less than 6 months of efficacy assessment in period 4 are not included in the PP

The list of subjects in PP is found in Appendix 4 section 7.4.

The FAS will be used for baseline tables and efficacy output and the SAF will be used for safety tables and listings. The PP will be used for a supportive analysis of the primary endpoint.

DPS	Description
DPS1	
 
Subjects who are treated in period 4 will be included.
 
Post-discontinuation data will not be included.
 

DPS2	
 
Only subjects who complete treatment in period 4 will be included.
 

The following data point sets are defined:

FAS and DPS1 are used to estimate the primary estimand for the primary endpoint and the primary estimand for the key secondary endpoints.

FAS and DPS2 are used to estimate the secondary estimand for the primary endpoint.

Type of document	Date:	11-Aug-2022	
Document ID	Version:	4.0	
	Status:	Final	
INTERNAL USE	Page:	28 of 79	

In addition, to investigate the impact of covid-19 (see section **3.2**), the following observation periods are defined:

OP	Description

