### 4.2.3 Main analytical approach

The primary endpoint, based on both the primary and secondary estimand, will be compared between treatment groups using the hypothetical estimand for the FAS population using either the DPS1 or DPS2, i.e. subjects for whom the primary endpoint is missing due to discontinuation of treatment prior to period 4 will not contribute to the analysis. This approach of using observed data only (an observed case analysis), implicitly assumes that observations are missing completely at random (MCAR), i.e. had the subjects continued treatment into the efficacy assessment period (period 4), they would have experienced the same treatment effect as subjects from the same treatment arm with observations of the primary endpoint. This assumption will be investigated in a sensitivity analysis.

The primary endpoint will be analysed by means of a negative binomial (NB) regression model with the number of asthma exacerbations as the response variable, treatment group, age group (<12 years/ $\geq$ 12 years) and region as fixed effects, and the logarithm of the time in period 4 (in years) as an offset value.

The between treatment group comparison will be performed using a Log Likelihood Ratio (LR) test derived from the NB regression analysis. The null hypothesis is that the rate of clinically relevant asthma exacerbations is equal for the active group and the placebo group. The alternative hypothesis is that the rate of clinically relevant asthma exacerbations is different for the active

Type of document Document ID	Date: Version:	11-Aug-2022 4.0	
	Status:	Final	
	гауе.	310179	

group and the placebo group. The main outcome is the resulting p-value from the LR test reported together with the ratio of the rates and Wald 95% confidence intervals.

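### The data point set used for the key secondary endpoints is tied to period 4, although their efficacy period starts at visit 5

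*SAP*

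**What the plan says.** SAP section 3 defines DPS1 with two rules: "Subjects who are treated in period 4 will be included", and data after discontinuation are left out. It then assigns the set: "FAS and DPS1 are used to estimate the primary estimand for the primary endpoint and the primary estimand for the key secondary endpoints".

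In SAP section 1.2, the text below Figure 1 fixes what period 4 means: "Period 4 is the efficacy assessment period for the primary endpoint", beginning on 1 September for all subjects.

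The estimand sections use another period for the key secondary endpoints. SAP 1.1.9.3 removes only subjects who stop treatment before the efficacy period, which it gives by endpoint as "period 4 for the primary endpoint and visit 5 to visit 11 for the key secondary endpoints". SAP 1.1.9.7 repeats this ("The efficacy period for the key secondary endpoints is defined as visit 5", running to visit 11) and adds: "Discontinuations in the efficacy period will be handled as for the primary estimand for the primary endpoint". For the primary estimand, that means using data up to the point of stopping.

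SAP Table 2 lists the analysis set for the key secondary endpoints as FAS and uses discontinuers' data as far as they were observed. It names no data point set, whereas Table 1 names DPS1 or DPS2 for each estimand of the primary endpoint. Protocol 15.8 bases the key secondary analyses on all FAS subjects who have observations of those endpoints.

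**The concern.** Two rules in the SAP give different answers for one group: subjects who attend visit 5 on treatment and then stop before 1 September. Under 1.1.9.3, 1.1.9.7 and Table 2 their visit 5 data, and sometimes their visit 6 data, belong in the analysis. Under section 3 they are outside DPS1 altogether.

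The three key secondary endpoints are in the alpha-controlled hierarchy (SAP 2.1), so the subjects analysed should not depend on which section a programmer follows. The subjects left out would be selected by an event after randomisation. For the primary endpoint, SAP 4.2.3 acknowledges that leaving out subjects who stop before period 4 assumes data missing completely at random, and it promises a sensitivity analysis. For the key secondary endpoints, SAP 4.3.1.4 plans none.

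There are two further inconsistencies. SAP 4.8 does not list the narrower set as a change from protocol 15.8. And the additional secondary endpoint, change from baseline in percentage predicted FEV1, uses FAS with no data point set (SAP Table 3) and the same type of model as the key secondary FEV1 endpoint. As written, the two FEV1 analyses could cover different subjects.

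**Working it through.** **Does visit 5 fall before period 4?**

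Inputs:
- Treatment starts between 1 November and 10 April (protocol 3.1).
- Period 4 starts on 1 September (protocol 3.1; SAP 1.2).
- Visit 5 is at 4 months and visit 6 at 8 months, each ±7 days, and a month counts as 30 days (flow chart in both documents). With R the randomisation date, visit 5 = R + 120 days and visit 6 = R + 240 days.

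The plan's own figure first, in a non-leap year (a leap year moves the dates before March by one day):
- R = 1 November: 304 days to 1 September, and 304/30 = 10.1 months.
- R = 10 April: 144 days to 1 September, and 144/30 = 4.8 months.

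This agrees with the stated 4 to 10 months for period 3.

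Visit 5, with gap to period 4 = (days from R to 1 September) − 120:
- R = 1 November: visit 5 on 1 March, gap 304 − 120 = 184 days.
- R = 10 April: visit 5 on 8 August, gap 144 − 120 = 24 days. With the +7-day window it is 15 August, gap 17 days.

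So visit 5 precedes period 4 for every start in the window, not only for early starts. Protocol 3.3 has a looser limit, randomisation before 1 May. For R = 30 April, nominal visit 5 is 28 August, still before period 4, but the +7-day window reaches 4 September.

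Visit 6 precedes 1 September if R is at least 241 days earlier, that is, up to about 3 January.

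**How many subjects could be affected?**

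Protocol Table 14 (site 613 excluded) gives subjects randomised and subjects in period 4:
- Cohort 1: 76 − 72 = 4 did not enter period 4.
- Cohort 2: 249 − 244 = 5 did not enter.
- Together: 9 of 76 + 249 = 325, or 2.8%.
- Cohort 3: 199 randomised, no period 4 count given.

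The 9 include anyone who stopped before visit 5. Those subjects have no data at visits 5 to 11 under either rule, so 9 is an upper bound for cohorts 1 and 2.

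For the whole trial, 533 randomised less the 9 subjects at site 613 leaves 524 (= 76 + 249 + 199). The share of non-entrants who stopped after visit 5 is not given. The table takes 25% to 75% as an assumption.

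| Rate of not entering period 4 | Non-entrants of 524 (upper bound) | Affected if 25% to 75% stopped after visit 5 |
|---|---|---|
| 2.8% (cohorts 1 and 2, assumed for cohort 3) | 14.5 | 3.6 to 10.9 (0.7% to 2.1%) |
| 10% (planning ceiling, protocol 15.13) | 52.4 | 13.1 to 39.3 (2.5% to 7.5%) |

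Subjects who reach period 4 on treatment satisfy DPS1 and keep their visit 5 and visit 6 data.

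**The case against.** The strongest reply is that this is loose wording and no data would be lost in practice. SAP 1.1.9.3, 1.1.9.7, 4.3.1.3 and Table 2 all point to FAS with visits 5 to 11. The word 'only' appears in the definition of DPS2 but not in that of DPS1. SAP 1.1.9.6 also shows that the SAP is willing to redefine period 4 for a particular estimand. On that view, period 4 in DPS1 simply means the efficacy period of whichever endpoint is analysed.

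Part of this stands: the loss occurs only if DPS1 is applied as written. The rest does not remove the conflict. SAP 1.2 ties period 4 to the primary endpoint. The redefinition in 1.1.9.6 is explicit, changes only the end of the period, and has no counterpart for the key secondary endpoints. The SAP itself treats DPS1 and DPS2 as excluding rules, since in 4.2.3 "subjects for whom the primary endpoint is missing due to discontinuation of treatment prior to period 4 will not contribute to the analysis". That Table 2 names no data point set does not cancel the explicit assignment in section 3.

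A second reply is that the remedy also selects after randomisation, because subjects who stop before visit 5 stay out. That is true. It follows from the estimand the SAP has chosen, and the remedy only brings the data point set into line with it.

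A reader might also infer a bias between arms from early local reactions to active treatment. The documents do not support this. Protocol 1.2 describes these reactions as typically arising in the first one to two days. A subject who stopped because of them would usually be gone well before visit 5 and would have no data under either rule. Protocol 5.1 does make some asthma events a reason to stop treatment, so the affected subjects need not be a random subset. But nothing in the documents shows that their number or outcomes differ by arm.

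**Conclusion.** The inconsistency is real and minor. Section 3 sets a rule for the key secondary endpoints that contradicts the estimand it is meant to serve and departs from protocol 15.8 without being listed in SAP 4.8. Applied as written, it would drop on-treatment visit 5 data, and visit 6 data for subjects randomised up to about 3 January, of those who stop between visit 5 and 1 September.

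The size is at most 9 of 325 subjects (2.8%) in cohorts 1 and 2. The true number is unknown and may be zero. This reads the period 4 counts in protocol Table 14 as subjects still on treatment. SAP 1.1.9.3 reports only 3 subjects who stopped treatment without leaving the trial at that time, so little turns on it. Carrying the rate over to cohort 3 is an assumption, since that cohort's period 3 overlapped the pandemic and protocol 15.2.2 expects that discontinuation may have risen.

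Two stronger conclusions should not be drawn: that data have been lost, and that the treatment comparison is biased.

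**What to change.** Define DPS1 by endpoint in SAP section 3:
- Primary endpoint: subjects treated in period 4.
- Key secondary endpoints: FAS subjects with at least one on-treatment observation at visits 5 to 11.
- Both: no data after treatment discontinuation.

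Then add the data point set to Table 2, as Table 1 already does. The cost is one table row and one table column, with no new data and no change to the models or the test order. The SAP states that it was approved before database lock and unblinding, and the edit should be made before those steps. If they have passed, the interpretation used should be recorded in the trial report, where protocol section 15 places departures from the final SAP.

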### 3.2 Impact of Covid-19

Covid-19 has impacted the trial in terms of both recruitment opportunities and impact on the primary endpoint, see section **5.1**.

Additional statistical analyses of the primary endpoint (see section **4.2.6**) and the key secondary endpoints (see section **4.3.1.6**) are performed to analyse the impact of Covid-19.

### 4 STATISTICAL ANALYSES

Statistical analyses will be carried out by ALK, Biometrics, Hørsholm, Denmark. All computations will be performed using the statistical analysis system SAS® version 9.4 or later.

The analyses described in this section, along with the supporting information supplied in the Appendices (7.1 and 0), specify the statistical analyses.

### 4.1 General considerations

If nothing else is mentioned, all the statistical tests described in this section use a significance level of 5% and all tests and confidence intervals are 2-sided. The null hypothesis is the hypothesis of no difference and the alternative to the null hypothesis is the hypothesis of difference.

Descriptive statistics for numerical variables include summary tables displaying mean, SD, median, minimum and maximum and relevant quantiles. Descriptive statistics for categorical variables include frequency tables that display numbers and percentage.

When age is used as fixed effect in the statistical models, it is the age assessed at randomisation that is used.

Type of document	Date:	11-Aug-2022	
Document ID	Version:	4.0	
	Status:	Final	
INTERNAL USE	Page:	29 of 79	

If baseline measurements are missing for any efficacy endpoints, the last measurement before or on the date of first treatment will be used, if possible, for the given endpoint (screening observation carried forward).

In addition, all efficacy endpoints will be presented in summary tables.

### 4.1.1 Considerations regarding countries/region

Variation between countries/region in the primary endpoint is expected and may result from variation in geography and thus HDM exposure, variation in standard treatment procedures and from possible differences in conduct of the trial protocol. Variation between sites (centres) is also expected but is assumed to be small compared to the variation between countries and regions.

To ensure a balanced dataset for the primary endpoint, countries are pooled to regions. Three regions are defined (west: DEU, ESP, FRA, GBR and USA; central: POL; east: BGR, HUN and RUS). The region variable is used instead of country for all analyses, where a country/region factor is applied.

### 4.1.2 Model assumptions

Model checking of the models used in the test hierarchy, see section **2.1**, will be performed based on visual inspections of residual plots (for the NB models and marginal models) and by visual inspections of quantile-quantile (QQ) plots (for the MMRM model).

### 4.2 Primary endpoint analysis

For the primary endpoint, data collected after treatment discontinuation is only used for sensitivity analysis 2. For all other scenarios, no data collected after treatment discontinuation is used.

### 4.2.1 Definition of endpoint

The primary endpoint of the trial is the annualised rate of clinically relevant asthma exacerbations calculated as the number of exacerbation events per subject year during the efficacy evaluation period (period 4).

Note that period 4 begins on September 1st for all subjects and lasts until the end of trial or discontinuation of IMP.

### 4.2.2 Overview of analyses of primary endpoint

**Table 1** gives an overview of the analyses of the primary endpoint including the handling of treatment discontinuations and missing data.

In the sensitivity analysis 1, the data from the discontinuations in period 3 (number of events and exposure time) are carried forward and used in period 4 (LOCF). Data for discontinuations in period 4 are included as observed.

In the sensitivity analysis 2, subjects are not included if they discontinue in period 3. Data for discontinuation in period 4 are included as observed together with data imputed from placebo completers.

Type of document	Date:	11-Aug-2022	
Document ID	version:	4.0	1990.00 A
	Status:	Final	
INTERNAL USE	Page:	30 of 79	

# Table 1 Overview of analyses and handling of discontinuations and missing data for the primary endpoint

Analysis	Estimand	Analysis set/DPS	Impact of Covid-19 effect included	Statistical method	Treatment discontinuation approach/ Missing data approach	
					Discontinuations in period 3	Discontinuations in period 4
Primary	Primary	FAS/ DPS1	1) None 2) OP1, OP2	NB regression	Not included/ None	Included as observed/ None
	Secondary	FAS/ DPS2	1) None 2) OP1, OP2	NB regression	Not included/ None	Not included/ None
Sensitivity 1	N/A	FAS	1) None	NB regression	Included as observed/ LOCF	Included as observed/ None
Sensitivity 2	N/A	FAS	1) None	NB regression	Not included/ None	Included as observed/ Imputed from placebo completers
Supportive	Primary	PP/ DPS1	1) None	NB regression	Not included/ None	Included as observed/ None

None = no Covid-19 effect analysed, LOCF = Last Observation Carried Forward, OP1 = trial observation period before and including 20-Mar-2020 (before Covid-19), OP2 = trial observation period after 20-Mar-2020 (during Covid-19), OP1, OP2 = a Covid-19 effect is applied representing either the period before or during Covid-19. Included as observed = only observed data in the part of the period in which they are collected are used. If discontinuations occur, the observed values are included.

### 4.2.3 Main analytical approach

The primary endpoint, based on both the primary and secondary estimand, will be compared between treatment groups using the hypothetical estimand for the FAS population using either the DPS1 or DPS2, i.e. subjects for whom the primary endpoint is missing due to discontinuation of treatment prior to period 4 will not contribute to the analysis. This approach of using observed data only (an observed case analysis), implicitly assumes that observations are missing completely at random (MCAR), i.e. had the subjects continued treatment into the efficacy assessment period (period 4), they would have experienced the same treatment effect as subjects from the same treatment arm with observations of the primary endpoint. This assumption will be investigated in a sensitivity analysis.

The primary endpoint will be analysed by means of a negative binomial (NB) regression model with the number of asthma exacerbations as the response variable, treatment group, age group (<12 years/ $\geq$ 12 years) and region as fixed effects, and the logarithm of the time in period 4 (in years) as an offset value.

The between treatment group comparison will be performed using a Log Likelihood Ratio (LR) test derived from the NB regression analysis. The null hypothesis is that the rate of clinically relevant asthma exacerbations is equal for the active group and the placebo group. The alternative hypothesis is that the rate of clinically relevant asthma exacerbations is different for the active

Type of document Document ID	Date: Version:	11-Aug-2022 4.0	
	Status:	Final	
	гауе.	310179	

group and the placebo group. The main outcome is the resulting p-value from the LR test reported together with the ratio of the rates and Wald 95% confidence intervals.

